Inclusion of Minorities and Women: Describe efforts to include minorities and women. If either minorities or women are excluded, include a justification for the exclusion.

Minorities and women will be included without discrimination.

Inclusion of Children: Describe efforts to include children. Inclusion is required unless a clear and compelling rationale shows that inclusion is inappropriate with respect to the health of the subjects or that inclusion is inappropriate for the purpose of the study. If children are included, the description of the plan should include a rationale for selecting or excluding a specific age range of children. When included, the plan must also describe the expertise of the investigative team in working with children, the appropriateness of the available facilities to accommodate children, and the inclusion of a sufficient number of children to contribute to a meaningful analysis relative to the purpose of the study. Provide target accrual for this population. Identify whether children are wards of the state. **If children are excluded** then provide appropriate justification.

Children are excluded because we will be studying an adult-sized neck wrap.

For protocols including the use of an investigational drug, indicate whether women of childbearing potential have been included and, if not, include appropriate justification.

N/A

If HIV testing is included specifically for research purposes explain how the test results will be protected against unauthorized disclosure. Include if the subjects are to be informed of the test results. If yes, include the process and provision for counseling. If no, a rationale for not informing the subjects should be included.

Not applicable

Will the SONA Psychology Pool be utilized? *Include documentation indicating permission to use this recruiting tool*

Yes No

FINANCIAL CONSIDERATIONS

Describe all potential research related expenses to subjects:

None.

Compensation for participation: Describe all plans to pay subjects, either in cash, a gift or gift certificate. Please note that all payments must be prorated throughout the life of the study. The IRB will not approve a study where there is only a lump sum payment at the end of the study because this can be considered coercive. The amount of payment must be justified. Clarify if subjects will be reimbursed for travel or other expenses.

Not applicable

Subjects will be given \$125 after their first intervention and \$125 after their second intervention in the form of a check(s). Each visit will take approximately 2.5-3 hours, plus travel time, making this an appropriate amount.

Research Data Management Plan: The Research Data Management and Security Plan form must be completed. The form, along with guidance, can be found in our [forms library](#) and must be submitted with your initial application.

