When the subject has no further questions, the study coordinator will measure the subject's height, weight, and neck circumference. Next, the MR technologist will review the MRI Safety Questionnaire then escort the subject into the MRI suite and help them lie on the MRI scanner bed. Once on the scanner bed the MR technologist will apply the adhesive wrap to the subject's neck (Bard product code 318-01-04). Two fiber optic thermometers will be used to measure surface temperature. One will be embedded in an ear plug which will be gently inserted into one of the subject's ears in order to measure tympanic membrane (ear drum) temperature. The other will be placed under the neck wrap between the wrap and the surface of the skin in order to measure the subject's neck skin temperature. Both the neck wrap and the fiber optic thermometers are MRI compatible. In order to keep the Arctic Sun cooling device outside the MRI suite, a 25-foot insulated tubing set, which does not contain metal, will be used. The tubing will go from the Arctic Sun cooling device in the control room, through a wave guide in the wall between the control room and the MRI suite, to the wrap on the subject's neck. A similar cooling set up has been used previously by the same investigators at our institution.

A standard MRI compatible set up will be used to measure the subject's vital signs, including heart rate and blood pressure at 15-minute intervals throughout the study. A modified bedside shivering assessment will be completed by the study coordinator every 30 minutes and a blanket will be offered to the subject if mild shivering is detected, or if the subject requests it. 60 minutes into the intervention the MR technologist will conduct a "skin check," examining the subject's skin under the wrap.

The subject will stay in constant communication with the MR technologist and study coordinator using a 2-way intercom system throughout the study. As an additional safety measure, the subject will also have a squeeze ball in their hand which sets off an alarm in the control room.

At this point, the subject will be ready to undergo their first intervention.

The subject will then be randomized to either the cold or body-temperature study arm using a sealed envelope system. The subject will be informed which arm of the study they were randomized to.

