The intervention will start when the subject indicates they are ready to begin. At the beginning and end of each intervention, an MRI technique called pCASL will be used to quantify blood flow to the brain. MR thermometry will be used throughout the two hour intervention to measure core brain temperature every ~1 minute. The Arctic Sun will be operated in manual mode. By operating in manual mode, the study coordinator can set the temperature of the circulating water on the device touch screen. Regardless of which study arm the subject is in, the water temperature will be started at body-temperature (37°C).

Note: The Arctic Sun device will be operated by the study coordinator for the duration of the study. Bard will provide training on how to operate the device prior to enrollment and will be available for technical support should it be needed.

In the **body-temperature** arm, the water temperature will be left at 37°C for the duration of the study.

In the **cold arm**, over ~5-10 minutes, the study coordinator and the subject will lower the temperature of the circulating water to find the lowest tolerable temperature. The circulating water will be kept at this temperature for the remainder of the 2-hour intervention unless the subject indicates they would like to adjust the temperature of the circulating water (either up or down). The subject can adjust the temperature of the circulating water as many times as desired during the intervention. The subject's skin temperature will be constantly monitored, and recorded, using the fiber optic thermometer discussed earlier, and will never be allowed to drop below 6°C. This lower limit for skin temperature was selected based on the fact that lower skin temperatures are associated with a phenomenon known as the Hunting reaction, a protective but painful response of the skin in which vasodilation and vasoconstriction occur (Daanen H. Finger cold-induced vasodilation: a review. European journal of applied physiology. 2003; 89(5):411-426).

At the conclusion of each intervention, the subject will complete a 5-minute questionnaire about their experience including open-ended questioning to identify any adverse effects experienced.

A second intervention will be scheduled, ideally within the following 7 days.

The study coordinator will complete a COVID-19 Assessment 24-48 hours prior to their second visit to confirm eligibility to come to campus.

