The second intervention will be identical to the first. If the subject was randomized to the cold intervention for their first visit they will cross over to the body temperature intervention for their second visit, and vice-versa.

The purpose of the body temperature intervention is to serve as a control for our cooling intervention in order to be certain that any change in brain temperature observed during the cooling intervention is due to the temperature of the circulating water.

Describe required screening procedures performed before enrollment and while on study.

When a subject responds to our recruitment materials, the study coordinator will review the Key Information portion of the Consent with the subject via phone or Zoom tele-video. Subjects who remain interested will be screened for study eligibility using an Eligibility Checklist. Eligible subjects will have the full Consent Form reviewed with them during a Zoom tele-video call. Ineligible subjects will be notified of the reasons for ineligibility and what will happen with the eligibility information they have already given using a script (see Eligibility Checklist for script).

Verbal permission to email the eConsent to the subject will be obtained using the following language: "Because UVM can't control the security of email messages once we send them, we need your permission to email you. Do you want to receive the link to the eConsent via email?"

Verbal permission will be documented in REDCap. The eConsent will be reviewed with the subject. The consent process will take approximately 25 minutes. The subject (and the study coordinator) will be able to sign the eConsent electronically. The fully executed consent will be available for the subject to download or, if they prefer, it will be emailed to them. The Consent Process Documentation form will be utilized to document consent.

For research involving survey, questionnaires, etc.: Describe the setting and the mode of administering the instrument and the provisions for maintaining privacy and confidentiality. Include the duration, intervals of administration, and overall length of participation.

Not applicable

1. **Eligibility Checklist (3 minutes):** The study coordinator will use this brief yes/no questionnaire when contacted by an interested subject to confirm study eligibility.

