2. **MRI Safety Questionnaire (3 minutes):** The MRI Safety Questionnaire has been implemented into the Eligibility Checklist to confirm safety to undergo an MRI. This form will be reviewed with the subject at their first and second visits to the MRI Research Center to confirm no changes have occurred since it was completed.
3. **Data Sheet (2.5 hours/intervention):** The study coordinator will complete the research Data Sheet at each visit. Subject height, weight, and neck circumference will be collected prior to starting the intervention and water temperature, skin temperature, vital signs, and bed side shivering assessment will be collected during the intervention. This data sheet also includes questions for the subject at the end of the intervention about their experience, including open-ended questioning to identify any adverse effects they may have experienced.

TYPES OF PROCEDURES (Please do not use the "other" option unless the procedure is not listed.)

Check all that apply.

Survey (mail, telephone, in-person, on-line)
Medical exams/history

Blood drawing:

Vol.

Over days, weeks?

Type & Amt.

	Deception *see below		Surgery		Collection of Urine and/or Feces
	Observation		Drug Administration		HIV Testing
	Photographs		Device Use		Ultrasound (e.g. echocardiogram)
	Audio Recording		Exercise		Imaging (e.g. CT scan, DEXA, mammogram, PET scans, SPECT)
	Video Recording		Diet		Use of Radiation treatment
	Interviews in person or by phone		Pathology Specimens (retrospective)		Use of Radioactive substances (e.g. radiolabeled antibodies, drugs or contrasts)
	Focus Groups		Genetic Materials (DNA)** see below		MRI (for treatment studies)
	Review of prospective data		Questionnaires		MRI (not for treatment studies)

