We will minimize risk of loss of autonomy by following standard procedures for obtaining informed consent. We will begin this process when an interested subject calls to express interest in participating by reviewing the Key Information section of the Consent to clarify why the study is being performed, what would be required of them, and the risks and benefits associated with participation. We will emphasize that subject participation (or lack thereof) has no impact on the medical services they will receive and subjects will be reminded there is no penalty for withdrawing from this study.

We will minimize risk of loss of confidentiality and privacy by having all information collected and handled by research staff trained to deal appropriately with sensitive clinical issues. All study information will be treated as confidential and will be available only to research staff and the study sponsor (Bard Medical Division). All data given to the study sponsor will be de-identified. All paper records will be kept in a locked office at UVM/UVM-MC. Electronic records will be stored behind the UVM/UVM-MC firewall. When contacting participants for follow-up, no identifying information other than the first name of the research assistant will be used when leaving messages or speaking to anyone other than the participant him/herself. No information about participants will be released without their permission or where required by law.

Benefits

There are no direct benefits to the subject. There are benefits to society. Because most currently available devices to cool the brain **also** cool the rest of the body and generally require sedation to be tolerated, they can only be used for select conditions in an intensive care setting, and have negative consequences on other organ systems. The goal of this research is to develop a device that non-invasively, selectively cools the brain and could be used in awake patients with critical and non-critical conditions without cooling the rest of the body.

Risk/Benefit ratio

We believe the risk/benefit ratio favors performing this study as the associated risks are small and reversible, while the potential benefit is large.

Therapeutic Alternatives: List the therapeutic alternatives that are reasonably available that may be of benefit to the potential subject and include in the consent form as well.

Not Applicable

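### Adverse effects are asked about only as each session ends; no planned question covers effects that appear after the subject has left, and nothing is scheduled after visit 2.

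*Combined protocol and SAP*

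**What the plan says.** Procedures sets the timing of adverse-effect questioning: "At the conclusion of each intervention, the subject will complete a 5-minute questionnaire about their experience". That questionnaire carries the open-ended questions on adverse effects. The description of the Data Sheet, in the list of study instruments, agrees: "This data sheet also includes questions for the subject at the end of the intervention about their experience".

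The second visit follows soon after the first: "A second intervention will be scheduled, ideally within the following 7 days". The one contact described between visits has a different purpose: "The study coordinator will complete a COVID-19 Assessment 24-48 hours prior to their second visit". On arrival at visit 2 the MRI Safety Questionnaire is reviewed for changes.

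Order is set by envelope ("The subject will then be randomized to either the cold or body-temperature study arm using a sealed envelope system") and then reversed on the return appointment: "If the subject was randomized to the cold intervention for their first visit they will cross over to the body temperature intervention for their second". The opposite switch applies to anyone who starts with the body-temperature session, so those subjects end the study with the cold one.

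The only mention of follow-up contact is a confidentiality rule under Risks/Benefits: "When contacting participants for follow-up, no identifying information other than the first name of the research assistant will be used" in messages or in speaking to third parties. Under Data Safety and Monitoring, the principal investigator reviews the Data Sheet after each intervention, and a serious adverse event suspends the study.

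**The concern.** Skin damage is the first risk listed under Risks/Benefits, and the planned protections against it act before or during the session. An effect that becomes apparent hours or days later falls outside all of them and outside the end-of-session questionnaire.

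Three parts of the plan depend on such information arriving. The principal investigator's review works from the Data Sheet. The suspension rule needs someone to learn of a serious event. The tolerability assessment after the first three subjects feeds a decision on whether to lengthen the session. None of these has a planned source for events after a session. A subject with a late problem would not be asked about it, and the report of the study could not say that delayed effects had been looked for.

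**Working it through.** **The plan's own figures.** The protocol gives no figure for adverse-effect ascertainment. Its one calculation is the sample size in Statistical Considerations: significance level 0.05, power 0.90, SD 0.8 °C, change 0.8 °C, 13 subjects needed, 15 enrolled. The standardised effect is 0.8/0.8 = 1.0. For a paired t test, taken as two-sided, power comes from the noncentral t distribution with n − 1 degrees of freedom and noncentrality 1.0 × √n. It is 0.883 at n = 12 and 0.911 at n = 13, so 13 is reproduced. Nothing below changes it.

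**Contacts by sequence.** Setting Procedures, the instrument list and Data Safety and Monitoring side by side:

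| Point in the study | Cold session first | Cold session second | Is an adverse-effect question described? |
|---|---|---|---|
| During each session | Intercom, squeeze ball, vital signs every 15 min, shivering assessment every 30 min, skin check at 60 min | Same | Monitoring only; cannot see later effects |
| End of session 1 | After cold | After body temperature | Yes |
| 24-48 h before visit 2 | COVID-19 assessment | Same | No |
| Start of visit 2 | MRI safety review | Same | No |
| End of session 2 | After body temperature | After cold | Yes |
| After visit 2 | Nothing scheduled | Nothing scheduled | No |

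Two facts follow. First, no row describes asking any subject about the time since an earlier session. Cold-first subjects do complete a second questionnaire, but as described it concerns the session just finished. Second, cold-second subjects have no scheduled contact of any kind after cooling.

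**How many subjects.** The first fact applies to all 15. For the second, the protocol states neither allocation ratio nor blocking, so 1:1 is an assumption. The expected number is 15 × 0.5 = 7.5, that is 7 or 8. If the envelopes were unblocked, the count would be Binomial(15, 0.5), with a central 95% range of 4 to 11.

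**What asking everyone would support.** If n subjects are asked and none reports a delayed effect, the one-sided 95% upper limit on its rate is 1 − 0.05^(1/n). For n = 15 this is 18.1%; for n = 13, the number left after the losses the protocol allows for, it is 20.6%. Under the plan as written, no such limit can be calculated, because the number of subjects known to have been asked is zero.

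**The case against.** The best defence is that skin risk is already handled with care: exclusions, continuous skin-temperature recording with a stated floor, constant intercom contact, a skin check at 60 minutes, open-ended questions, and investigator review after every session. Subjects can also report a problem unprompted, and the investigator must address unanticipated problems for as long as the study runs. The consent pages were removed and the Data Sheet form is not included, so an instruction to report late symptoms may exist. Most of this stands, and it keeps the point at the level of a worthwhile improvement. It does not close the gap: in-session measures cannot see what appears later, and an invitation to report is not the same as being asked. The follow-up phrase under Risks/Benefits gives no time, purpose or content, so it does not establish a contact after visit 2.

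A reader might infer that cold-first subjects are asked about delayed effects and cold-second subjects are not, so that ascertainment depends on randomised order. The documents do not support this, because no such question is described for either sequence. What differs is only whether any scheduled contact follows the cold session.

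A reader might also infer a biased comparison of adverse effects between cold and body-temperature sessions. That does not follow. Every subject has both sessions, and a body-temperature session that comes second also has no later contact. With roughly balanced order, the two conditions are affected about equally. Nor does the protocol plan such a comparison: its outcomes are brain temperature and its relation to body characteristics.

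**Conclusion.** The point holds in limited form. As written, no planned question covers effects arising after a session, for any of the 15 subjects. For the 7 or 8 expected to have the cold session second (assuming 1:1 order), there is also no scheduled contact afterwards. A delayed effect would come to light only if a subject volunteered it. This rests on the visible text; the consent pages and the Data Sheet form could add reporting instructions.

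Two further readings should be avoided. The Risks/Benefits statement that risks are minor and recoverable is a justification made before the study, so it does not rest on the adverse-effect data the trial will collect. And no probability of detecting or missing a delayed effect can be derived: the documents give no event rate, and being contacted for another purpose is not being asked. The gap does not affect the primary analysis or the sample size, and its priority is low.

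**What to change.** Three changes, all to data collection; none alters a cooling or clinical rule.

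1. Add the existing open-ended adverse-effect question to the coordinator's contact before visit 2 and again at the start of visit 2, worded to cover the time since session 1.
2. Add one short coordinator call 24-48 hours after visit 2, with the same question.
3. Record each answer on the Data Sheet against the session it follows, with the interval since that session, so that it reaches the principal investigator's review.

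The interval matters because the timing will not be uniform. With a 7-day gap, the contact before visit 2 falls 7 − 2 = 5 to 7 − 1 = 6 days after session 1, whereas the final call comes at 1 to 2 days. Recording it will not equalise the windows, but will let them be reported honestly.

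The cost is about 15 calls of five minutes, 15 × 5 = 75 minutes of existing coordinator time. The other questions use contacts already planned. Enrolment stays at 15.

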Study Design: Describe the research design, including a description of any new methodology and its advantage over existing methodologies.

This is a randomized paired cross-over study in which each subject will undergo MR thermometry with and without active cooling to assess the effect of surface neck cooling on brain temperature.

Procedures: Describe all procedures (sequentially) to which human participants will be subjected. Identify all procedures that are considered experimental and/or procedures performed exclusively for research purposes. Describe the types, frequency and duration of tests, study visits, interviews, questionnaires, etc.

Note: A clinical research protocol may involve interventions that are strictly experimental or it may involve some aspect of research (e.g., randomization among standard treatments for collection and analysis of routine clinical data for research purposes). It is important for this section to distinguish between interventions that are experimental and/or carried out for research purposes versus those procedures that are considered standard therapy. In addition, routine procedures performed solely for research purposes (e.g., additional diagnostic/follow-up tests) should be identified.

Once a subject has been consented, they will schedule a visit at the UVM MRI Center for Biomedical Imaging. The study coordinator will contact the subject 24-48 hours prior to the scheduled visit to complete a COVID-19 Assessment to confirm eligibility to come to campus. After safety to come to campus is confirmed, the study coordinator will meet the subject at an agreed upon location at the UVM Medical Center (e.g. the lobby of the MRI Research Center). Once at the MRI Research Center they will review the MRI Safety Questionnaire and ask whether any changes have occurred since it was completed. All questions will be answered before proceeding.

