	Review of retrospective data		Diaries		Tissue (obtained for clinical purposes)
	Recording of Identifiable Data		Pregnancy Tests		Tissue (obtained solely for research)
	Electrocardiograms				
	Sensitive Data (criminal or sexual conduct, drug or alcohol conduct or use)			(specify):	

**If genetic information is being collected, GINA language must be added to the consent form.

*Deception typically involves withholding information from the potential subject and would require an alteration to the consent process.

Statistical Considerations: Delineate the precise outcomes to be measured and analyzed. Describe how these results will be measured and statistically analyzed. Delineate methods used to estimate the required number of subjects. Describe power calculations if the study involves comparisons. Perform this analysis on each of the primary and secondary objectives, if possible.

Primary outcome: Change in brain temperature

The analytic goal is to describe the change in brain temperature with application of cooling. Brain temperature is a continuous variable. We will use a difference-of-differences model where each subject contributes changes in brain temperature both with and without active cooling where:

$$\Delta T_k = (T_{CE,k} - T_{CB,k}) - (T_{WE,k} - T_{WB,k})$$

ΔT_k = net change in brain temperature for subject k

$T_{CE,k}$ = ending brain temperature, cold intervention for subject k

$T_{CB,k}$ = beginning brain temperature, cold intervention for subject k

$T_{WE,k}$ = ending brain temperature, warm intervention for subject k

$T_{WB,k}$ = beginning brain temperature, warm intervention for subject k

$$H_0: \sum \Delta T_k \neq 0$$

Assuming a significance level of 0.05, power of 0.90, and standard deviation of 0.8 °C (twice the size of previously published values^{Ref}), Student t test requires 13 subjects to detect a change of 0.8 °C. We plan to enroll 15 subjects to allow for loss to follow-up between the two visits.

Ref: Curran EJ, Wolfson DL, Watts R, Freeman K. Cold Blooded: Evaluating Brain Temperature by MRI During Surface Cooling of Human Subjects. *Neurocritical care*. 2017;27(2):214-219.

Secondary outcome: Describe how anthropomorphic characteristics affect change in brain temperature

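### Optional improvement, not an error: balance the cross-over order and average the two sequence means, so that a visit difference drops out of the ΔT estimate and its error term

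*Combined protocol and SAP*

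**What the plan says.** - Study Design: "This is a randomized paired cross-over study in which each subject will undergo MR thermometry with and without active cooling".
- Procedures: each subject is "randomized to either the cold or body-temperature study arm using a sealed envelope system". Allocation is open: "The subject will be informed which arm of the study they were randomized to".
- Procedures, on the second visit: "A second intervention will be scheduled, ideally within the following 7 days", and "The second intervention will be identical to the first". A subject "randomized to the cold intervention for their first visit they will cross over to the body temperature intervention for their second visit", and the reverse holds for the other order.
- Statistical Considerations, Primary outcome: "We will use a difference-of-differences model where each subject contributes changes in brain temperature both with and without active cooling where" ΔT_k = (T_CE,k − T_CB,k) − (T_WE,k − T_WB,k). With significance level 0.05, power 0.90 and SD 0.8 °C, described as double the published values, "Student t test requires 13 subjects to detect a change of" 0.8 °C. Fifteen are to be enrolled to cover losses between visits.

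The protocol does not say how the envelopes are prepared or whether the two orders are balanced. Student's t is named only in the sample-size sentence. That the analysis is a plain t test on ΔT_k without a visit term is the natural reading, because the formula contains none, but it is an inference.

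**The concern.** Subtracting each session's own starting temperature removes any visit-to-visit shift in baseline level. It does not remove a systematic difference between visits in how much temperature changes within a session. Call that difference π (visit 2 minus visit 1).

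Such a difference is plausible, though nothing in the documents sizes it. Subjects know their arm, choose how cold the water gets and may readjust it at will. Someone who has already spent two hours in the scanner wearing the wrap may behave differently the second time. If that affects only the cold session, the two orders still have different mean ΔT_k. A plain mean then weights them by the chance split, while the average of the sequence means weights them equally.

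The primary objective is descriptive, so the size of the estimate and its precision matter at least as much as the p-value. With 13 to 15 subjects, a visit difference would widen the interval and could move the estimate, and the planned analysis would not reveal it.

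**Working it through.** **Inputs.** From Statistical Considerations: effect 0.8 °C, SD of ΔT_k 0.8 °C, α 0.05 (taken as two-sided, which reproduces the stated N), 13 subjects needed, 15 enrolled. Assumed: π from 0 to 0.4 °C, because the documents give no figure.

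**1. The plan's own figure.** One-sample t test on ΔT_k: SE = 0.8/√13 = 0.2219, noncentrality 0.8/0.2219 = √13, 12 df. Power is 0.883 at n=12 and 0.911 at n=13, so 13 is correct. At n=15 power is 0.949.

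**2. What π does to ΔT_k.** With τ the cooling effect:
- cold first: mean ΔT_k = τ − π
- body temperature first: mean ΔT_k = τ + π

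Under 1:1 randomisation the SD of ΔT_k becomes about √(0.8² + π²). Given the realised split, the plain mean is shifted by π(n_warm-first − n_cold-first)/n.

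**3. Validity.** Under simple randomisation the expected shift is zero, and the simulated type I error of the plain t test is about 0.05 at every π tried.

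**4. Size of the shift.**
- Average absolute shift under simple randomisation: 0.226π at n=13 (0.07 °C at π=0.3) and 0.210π at n=15.
- At 9:4: 5/13 = 0.385π, or 0.115 °C at π=0.3. The probability of 9:4 or worse is 2(1+13+78+286+715)/8192 = 0.267.
- Balanced: 1/13 = 0.077π at 7/6 and 1/15 = 0.067π at 8/7, about 0.02 °C at π=0.3.

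**5. The alternative estimate.** Average the two sequence means: [(τ − π) + (τ + π)]/2 = τ, so π cancels at any split. SE = (SD/2)√(1/n₁ + 1/n₂), with n − 2 df.
- 7/6: 0.4√(1/7 + 1/6) = 0.2225; power 0.904
- 8/7: 0.4√(1/8 + 1/7) = 0.2070; power 0.946
- 8/5: 0.4√(1/8 + 1/5) = 0.2280; power 0.891
- 9/4: 0.4√(1/9 + 1/4) = 0.2404; power 0.857

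Under simple randomisation, its power averages 0.877 at n=13. It is therefore worth using only with a balanced order.

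**6. Comparison at n=13, with π added on top of SD 0.8** (simulation)

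| π (°C) | SD of ΔT_k | Power: simple randomisation, plain t | Power: 7/6, plain t* | Power: 7/6, sequence average | Mean 95% half-width: plain t / sequence average (°C) |
|---|---|---|---|---|---|
| 0 | 0.800 | 0.911 | 0.911 | 0.904 | 0.47 / 0.48 |
| 0.2 | 0.825 | 0.894 | 0.898 | 0.904 | 0.49 / 0.48 |
| 0.3 | 0.854 | 0.872 | 0.882 | 0.904 | 0.51 / 0.48 |
| 0.4 | 0.894 | 0.841 | 0.858 | 0.904 | 0.53 / 0.48 |

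*Mean over the two directions of π. This test is conservative: type I error 0.044 at π=0.2 and 0.031 at π=0.4.

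With all 15 completing, simple randomisation with plain t gives 0.949, 0.937, 0.920 and 0.896 at the same π; 8/7 with the sequence average gives 0.946 throughout.

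**7. Break-even.** Against simple randomisation with plain t, the sequence average gains once π exceeds about 0.12 °C (n=13) or 0.10 °C (n=15). Against a balanced order with plain t, the thresholds are about 0.14 and 0.12 °C.

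**The case against.** The strongest reply is that nothing is broken. Order is randomised, the test holds its level, N is right, and a t test on within-subject differences is a standard cross-over analysis. The whole benefit depends on a π that the documents neither quantify nor mention, in a design that plans identical sessions, ideally within a week. A π of 0.3 to 0.4 °C would be 75% to 100% of the implied published SD of 0.4 °C.

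The plan also carries margin. At SD 0.4, plain t at n=13 still has power 0.990 at π=0.5. At an assumed SD of 0.6 it has 0.958 at π=0.4. If the planning SD of 0.8 already includes π, plain t keeps 0.91. At small π the sequence average is slightly worse, and 8/5 after two losses falls to 0.891, just under the stated 0.90. Once the orders are balanced, the visit term adds little: at 8/7 and π=0.2, 0.946 against 0.941.

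All of this stands, and it is why the point is optional. It does not remove the case for the change. The trial already randomises order, so an estimate that does not depend on π being small is available for one degree of freedom. Silence about the envelopes does not show that they were unbalanced, and it gives no assurance that they were balanced.

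**Conclusion.** The point holds as a low-cost improvement to a valid analysis. It does not challenge the type I error, the sample size or the enrolment target; the smallest n giving 90% power with the sequence average is still 13.

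The gain depends on π, which is an assumption. It is nil at about 0.1 °C or less. At 0.3 °C on top of SD 0.8 and n=13, it is about 3 points of power (0.872 to 0.904), and the average absolute shift of about 0.07 °C is removed. At 0.4 °C it is about 6 points, with a half-width of 0.48 instead of 0.53 °C. If the true SD is nearer 0.4 °C, power is ample either way and the benefit is confined to the estimate and its interval. Neither analysis deals with carry-over between visits.

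**What to change.** (a) State how the sealed envelopes are prepared and balance the two orders 8/7 over the 15 subjects. Use one permuted list or blocks of undisclosed varying size, held by someone who does not enrol subjects. This alone removes most of the possible shift.

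(b) Together with (a), and not without it, make the primary estimate the average of the two sequence means of ΔT_k, with a 95% CI on n − 2 degrees of freedom. Keep the plain t test as a sensitivity analysis. A random-subject mixed model that brings in subjects with one visit is a different analysis and should be at most a further sensitivity analysis.

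Cost: envelope preparation and one or two sentences, with no extra subjects or scans. The downsides are:
- **One degree of freedom.** With no visit effect, power goes from 0.911 to 0.904 at 7/6 and from 0.949 to 0.946 at 8/7. If two losses leave 8/5, it is 0.891. With random losses from 8/7 that has probability 21/105 = 0.20; losses concentrated in the smaller sequence would make it more likely.
- **Some predictability, because allocation is open.** With a single 8/7 list, someone tracking allocations would know on average the last 8/8 + 7/9 = 1.8 assignments in advance, and three or more with probability 546/2730 = 0.20. Varying blocks of undisclosed size are the alternative to a single list.
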